4.2.1.2.3 Last Vaccination

Last vaccination before an unsolicited AE is derived from the start date of the unsolicited AE provided in the CRF and is calculated as follows:

- If an unsolicited AE has a complete start date and different to any of the vaccination dates, the start date is used to determine the last vaccination before the unsolicited AE.
- If the start date is missing or partially missing, or equal to any vaccination date, then the visit number in the “Appeared after Visit” or similar field, is used to determine the last vaccination before the unsolicited AE.

4.2.1.2.4 Time of Onset

Time of onset is derived from the start date of the unsolicited AE and the date of last vaccination as described in Section [4.2.1.2.3](#):

Time of Onset = start date of the unsolicited AE - date of last vaccination before the unsolicited AE + 1.

The time of onset is considered as missing only if one or both dates are missing or partially missing.

The unsolicited AEs will be analyzed “Within 30 days” after each vaccination, which corresponds to AEs with a time of onset between 1 and 31 days or missing. An AE with missing time of onset will be considered to have occurred just after the last vaccination (computed according to the Section 4.2.1.2.3), so will be included in these tables.

Time of onset period is computed as D1-D4, D5-D8, D9-D15, D16 or later, and Missing.

Note: Unsolicited AE that occurred before vaccination (negative time of onset) or with a time of onset higher than defined above will not be included in analysis but will be listed separately.

4.2.1.2.5 Duration

Duration is derived from the start and end dates of the unsolicited AE:

- Duration = End date of unsolicited AE - start date of unsolicited AE + 1.

The duration is considered as missing only if one or both of the start and end dates of the unsolicited AE is missing or partially missing.

4.2.1.2.6 Medically-Attended Adverse Event

Not applicable.

4.2.1.2.7 Serious Adverse Events

An event will be considered as a serious event if “Yes” is checked for “Serious” in the CRF.

SAEs will be analyzed throughout the study using the following periods:

- Within 30 days
- During post-Dose 1 period (i.e., after Visit 01 and within 30 days after the injection performed at Visit 01 for all groups)
- During post-Dose 2 period (i.e., after Visit 02 and within 30 days after the injection performed at Visit 02 for Group 1 or Group 2)
- During the study (i.e., all SAEs occurred during the study)

4.2.1.2.8 Adverse Events of Special Interest

An event will be considered as an AESI if “Yes” is checked for “Is the event an AESI?” in the CRF.

AESIs will be analyzed throughout the study using the following periods:

- Within 30 days
- During post-Dose 1 period (i.e., after Visit 01 and within 30 days after the injection performed at Visit 01 for all groups)
- During post-Dose 2 period (i.e., after Visit 02 and within 30 days after the injection performed at Visit 02 for Group 1 or Group 2)

- During the study (i.e., all AESIs occurred during the study)

4.2.2 Other Safety Endpoints

4.2.2.1 Pregnancy

This information will not be included in the analysis but will be listed separately. No derivation or imputation will be done.

4.2.2.2 Action Taken

This information will be summarized as collected, including missing observations. No derivation or imputation will be done.

4.2.2.3 Seriousness

This information will be summarized as collected. No derivation or imputation will be done.

4.2.2.4 Outcome

This information will be summarized as collected. No derivation or imputation will be done.

4.2.2.5 Causal Relationship

This information will be summarized as collected in the field “Relationship to IMP”. Missing causal relationship will be handled as described in Section [3.4.6.1.2](#). Relationship to study procedure is only presented in the listing.

4.2.2.6 Adverse Events Leading to Study Discontinuation

This information will be summarized as collected. A flag is available in the clinical database for all AEs in order to identify AEs leading to discontinuation before the end of active phase.

In general, the items that are counted are:

- Disposition table: A participant who, on the “Completion at End of Study” form question “What was the participant’s status?” has “Adverse Event” checked.
- Safety overview table: A participant who has either on the “Completion at End of Study” form, question “What was the participant’s status?” has “Adverse Event” checked or lists a solicited AE that has “Caused Study Termination” checked that is at least Grade 1 or an unsolicited AE that has “Caused Study Discontinuation” checked that is at least Grade 1 or missing and is within the time period indicated.
- System Organ Class (SOC)/Preferred Term (PT) table: A solicited AE that has “Caused Study Termination” checked that is at least Grade 1 or an unsolicited AE that has “Caused Study Discontinuation” checked that is at least Grade 1 or missing and is within the time period indicated.

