3.4.6.1.3 Intensity

For solicited reactions, missing intensities will be handled as described in [Section 4.2.1.1.1](#). For unsolicited AEs, missing intensities will remain missing and will not be imputed.

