4.2 Complementary Information on Derived Endpoints: Calculation Methods

4.2.1 Safety

4.2.1.1 Solicited Reactions

4.2.1.1.1 Daily Intensity

All daily records for solicited reactions will be derived into daily intensity according to the following classification: None, Grade 1, Grade 2, Grade 3, or Missing (Unknown).

For the derivation of daily intensities, the following sequential steps will be applied:

- 1) Solicited reactions (except Fever/Pyrexia) with CRF presence recorded as “No” and with all daily records missing (Unknown) then all daily intensities will be derived as None.
- 2) For non-measurable solicited reactions, daily intensities will correspond to daily records reported in the clinical database. For measurable solicited reactions the daily measurements reported in the clinical database will be converted based upon the intensity scales defined in the protocol; this assumes a reaction that is too large to measure (non-measurable, “NM”) is Grade 3. Note the intensity could be considered “None” (not a reaction) in the analysis despite being considered a reaction by the investigator (e.g., swelling measurement > 0 mm but < 25 mm in adults).

Note: The maximum intensity on the ongoing period is derived from the record of the maximum intensity/measurement after the end of the solicited period following the rule described above.

Table 4.1: Solicited injection site reactions: terminology, definitions, and intensity scales – Adolescents aged ≥ 10 to <17 years

CRF term (MedDRA LLT)	Injection site pain	Injection site erythema	Injection site swelling
Diary card term	Pain	Redness	Swelling

Definition	Pain either present spontaneously or when the injection site is touched or injected limb is mobilized	Presence of a redness including the approximate point of needle entry	Swelling at or near the injection site Swelling or edema is caused by a fluid infiltration in tissue or cavity and, depending on the space available for the fluid to disperse, swelling may be either soft (typically) or firm (less typical) to touch and thus can be best described by looking at the size of the swelling

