Intensity scale*	
CRF: Grade 1: A type of adverse event that is usually transient and may require only minimal treatment or therapeutic intervention. The event does not generally interfere with usual activities of daily living. Grade 2: A type of adverse event that is usually alleviated with additional therapeutic intervention. The event interferes with usual activities of daily living, causing discomfort but poses no significant or permanent risk of harm to the research participant. Grade 3: A type of adverse event that interrupts usual activities of daily living, or significantly affects clinical status, or may require intensive therapeutic intervention.
 
Diary card: Grade 1: No interference with usual activities Grade 2: Some interference with usual activities Grade 3: Significant; prevents usual activities
	Grade 1: ≥ 25 to ≤ 50 mm Grade 2: ≥ 51 to ≤ 100 mm Grade 3: > 100 mm	Grade 1: ≥ 25 to ≤ 50 mm Grade 2: ≥ 51 to ≤ 100 mm Grade 3: > 100 mm

LLT: lowest level term; MedDRA: Medical Dictionary for Regulatory Activities.

* For the subjective reaction of pain, participants or parents/legally acceptable representatives will record the intensity level (Grade 1, 2, or 3) in the diary card. For the measurable reactions of redness and swelling, they will record just the size of the reaction, and the classification as Grade 1, 2, or 3 will be assigned at the time of the statistical analysis.

Table 4.2: Solicited systemic reactions: terminology, definitions, and intensity scales – Adolescents aged ≥ 10 to < 17 years

CRF term (MedDRA LLT)	Fever	Headache	Malaise	Myalgia
Diary card term	Temperature	Headache	Feeling unwell	Muscle aches and pains
Definition	Elevation of temperature to $\geq 38.0^{\circ}\text{C}$ ($\geq 100.4^{\circ}\text{F}$)	Pain or discomfort in the head or scalp. Does not include migraine.	General ill feeling. Malaise is a generalized feeling of discomfort, illness, or lack of well-being that can be associated with a disease state. It can be accompanied by a sensation of exhaustion or inadequate energy to accomplish usual activities.	Muscle aches and pains are common and can involve more than one muscle at the same time. Muscle pain can also involve the soft tissues that surround muscles. These structures, which are often referred to as connective tissues, include ligaments, tendons, and fascia (thick bands of tendons). Does not apply to muscle pain at the injection site which should be reported as injection site pain.

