4.2.1.2 Unsolicited AEs

4.2.1.2.1 Presence

An observation will be considered an event if it has at least a verbatim term and is not a Grade 0 intensity event.

Grade 0 events are not included in safety analysis but are included in separate listings.

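### SAP 4.2.2.6 counts an ungraded unsolicited AE that ended participation but not an ungraded solicited reaction, so the SOC/PT table can only undercount

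*SAP*

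**What the plan says.** SAP 4.2.2.6 opens by saying that this item is reported as it was collected and that the database holds a discontinuation flag for every AE. It then defines three counts.

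- **Disposition table:** uses only the participant's status on the completion form.
- **Safety overview table:** uses that status or a flagged event.
- **SOC/PT table:** uses flagged events only.

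The flagged-event rule is the same in the last two: "a solicited AE that has “Caused Study Termination” checked that is at least Grade 1 or an unsolicited AE that has" its discontinuation box "checked that is at least Grade 1 or missing and is within the time period indicated". The solicited clause carries its own grade condition and has no allowance for a missing grade. The unsolicited clause has one.

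SAP 3.4.6.1.3 says: "For solicited reactions, missing intensities will be handled as described in" SAP 4.2.1.1.1. That section lists missing as a permitted daily value. Its only step for missing records covers a reaction, other than fever, whose CRF presence is recorded as No: "with all daily records missing (Unknown) then all daily intensities will be derived as None".

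Table 3.3 in SAP 3.4.3 plans a SOC/PT summary of all AEs leading to discontinuation, and of the related ones.

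**The concern.** The investigator's tick already records that the reaction occurred and that it ended participation. A derived-grade condition placed on top of that tick can remove an event but cannot add one. For a missing grade it removes solicited reactions alone, and these are treated by convention as related to vaccination (SAP 3.4.6.1.2). The SAP gives no reason for treating the two event types differently.

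Whether an AE led to early termination is among the items listed with the safety endpoints (Protocol Table 3.1, SAP Table 2.1). At stake are a SOC/PT table that does not deliver the full set Table 3.3 promises, and a possible participant in the disposition and overview tables with no SOC/PT row to explain the withdrawal.

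**Working it through.** The plan states no figure to reproduce. The check follows the rules through and then sizes one event.

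**Can a flagged solicited reaction lack a grade?**

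1. SAP 4.2.1.1.1: if CRF presence is not recorded as No and the daily records are missing, the daily intensities stay missing.
2. SAP 4.2.1.1.2: the overall intensity is the maximum of the daily intensities. With every day missing there is no grade to take. If some days are None and the rest missing, the SAP does not say which value results, but neither is Grade 1 or higher.
3. SAP 4.2.1.1.3: a missing maximum gives a missing presence, and the participant leaves the analysis of that reaction. The event is then in neither the solicited-reaction table nor the discontinuation SOC/PT table.

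So the case can arise under the SAP's own rules.

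**What does SAP 4.2.2.6 do with each flagged event?** The scale for erythema and swelling begins at "Grade 1: ≥ 25 to ≤ 50 mm", and a reaction too large to measure is Grade 3.

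| Flagged event | Derived intensity | In SOC/PT | In overview, form gives AE | In overview, form gives another reason |
|---|---|---|---|---|
| Solicited, no graded day | Missing | No | Yes | No |
| Solicited, 10 or 24 mm | None | No | Yes | No |
| Solicited, 25 or 50 mm | Grade 1 | Yes | Yes | Yes |
| Solicited, 60 mm | Grade 2 | Yes | Yes | Yes |
| Solicited, 101 mm or too large to measure | Grade 3 | Yes | Yes | Yes |
| Unsolicited, no grade | Missing | Yes | Yes | Yes |
| Unsolicited measurable, 10 or 24 mm | None | No | Yes | No |
| Unsolicited measurable, 25 mm or more | Grade 1 to 3 | Yes | Yes | Yes |

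The two event types differ only in the rows with a missing grade. Below 25 mm they are handled alike.

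Protocol 7.2 allows withdrawal by the participant or parent as a recorded reason, so the last column is possible. In that column a flagged, ungraded solicited reaction is in none of the three counts, because disposition also depends on the form.

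**Size of one event.** SAP 3.4.3 pools Groups 1 and 2 to keep the blind. Planned numbers are from SAP Table 1.1.

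- Pooled Groups 1 and 2: 174 + 174 = 348; 1/348 = 0.29%.
- Group 3: 1/116 = 0.86%.

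**The case against.** The strongest reply is that the case should be rare. One day at Grade 1 or higher is enough. Pain, headache, malaise or myalgia that does not interfere with activities is already Grade 1. Sites interview participants and clarify incomplete diary cards (Protocol 8.3.2). Early leavers are contacted for safety follow-up unless they refuse contact or are lost to follow-up (Protocol 7.2). AEs that caused discontinuation are followed until they resolve, stabilise or become chronic (Protocol 8.3.3). For an event to miss all three counts, the termination tick and the completion form must also disagree, which would normally raise a data query. All of this stands and limits the likely number. It does not change what the rule does with a case that remains.

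Four stronger readings are tempting, and the documents do not support them.

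- **Reactions under 25 mm are treated unequally.** SAP 4.2.1.1.1 does say of measurable reactions: "Note the intensity could be considered “None” (not a reaction) in the analysis despite being considered a reaction by the investigator". SAP 4.2.1.2.2 applies the same scale to measurable unsolicited events, so this loss comes from the grading scale and falls on both types. The remaining difference is in listing. For unsolicited events, "Grade 0 events are not included in safety analysis but are included in separate listings" (SAP 4.2.1.2.1); for solicited ones the SAP names no listing.
- **Participants who leave are likely to have no graded days.** No document says so, and the follow-up provisions above point the other way.
- **The Grade 0 exclusion hides SAEs or AESIs.** The size filter reaches only measurable terms on the solicited list. None of the four AESIs in Protocol 8.3.6 is such a term, and SAP 4.2.1.2.7 and 4.2.1.2.8 identify SAEs and AESIs by their CRF box.
- **One event is 1/174 of a group.** This SAP does not tabulate Groups 1 and 2 separately.

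A further objection is that counting a reaction derived as None would clash with SAP 4.2.1.1.3, which treats None as no presence. That is right, and it is why such reactions should be listed and not counted. A missing grade raises no such clash, because the solicited table does not report that reaction as absent.

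**Conclusion.** The point holds in a narrow form. As written, SAP 4.2.2.6 leaves a flagged solicited reaction with no graded day out of the SOC/PT table, and out of the overview unless the completion form gives an adverse event, while an ungraded unsolicited AE is kept. This is at odds with the section's own statement that the item is reported as collected and with the scope of Table 3.3. Any error is downward.

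Each affected participant is 0.29% of pooled Groups 1 and 2 or 0.86% of Group 3, assuming the safety sets equal the planned 348 and 116. No total effect can be calculated because the documents give no frequency for flagged, ungraded reactions, and it may be zero. This SAP covers the pooled, blinded safety analysis, and neither the primary objective nor any other immunogenicity analysis is affected.

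**What to change.** In SAP 4.2.2.6, in both the safety overview and the SOC/PT bullets, let the solicited clause accept a missing grade as the unsolicited clause does, and show the grade as missing. Add a separate listing of any flagged solicited reaction whose derived intensity is None, such as erythema or swelling under 25 mm, matching what SAP 4.2.1.2.1 already provides for unsolicited Grade 0 events.

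The cost is a few words in two bullets, a small programming change and one listing, with no new data. The discontinuation count could rise slightly. The change will not make all three tables agree in every case, because disposition still rests on the completion form and the SOC/PT table on the event flags. A tick that disagrees with the form remains a matter for data query.

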4.2.3 Immunogenicity

Not applicable for SMT analysis.

4.2.4 Efficacy

Not applicable for SMT analysis.

4.2.5 Derived Other Variables

4.2.5.1 Age for Demographics

The age of a subject in the study is the calendar age in years at the time of inclusion. It is displayed as an integer.

4.2.5.2 Duration of a Subject in the Trial

The duration of a subject in the study until last visit is computed in days as follows:

Maximum (Visit dates, Termination date) – V01 date +1

4.2.5.3 Duration of the Study

The duration of the study until last visit is computed as follows:

Maximum of all subjects (Visit dates, Termination date) – minimum for all subjects (V01 date) + 1

4.2.5.4 Time Interval

The time interval between 2 study timepoints (visits/vaccination/blood samples) is computed as follows:

Later date – earlier date.

5 Changes in the Conduct of the Trial or Planned Analyses

Not applicable.

6 Supporting Documentation

6.1 Appendix 1 List of Abbreviations

4vHPV	4-valent human papilloma virus
9vHPV	9-valent human papilloma virus
AE	adverse events
AESI	adverse events of special interest
AR	adverse reaction
CI	confidence interval
D	day
DMC	Data Monitoring Committee
DNA	deoxyribonucleic acid
ECDC	European Center for Disease Prevention and Control
EEA	European Economic Area
EMA	European Medicines Agency
EU	European Union
FAS	Full analysis set
FHA	filamentous hemagglutinin
FIM	fimbriae types 2 and 3
FSH	follicle stimulating hormone
GCI	Global Clinical Immunology
GCP	Good Clinical Practice
GM	Geometric mean
GMT	Geometric mean of titer
GMC	Geometric mean of concentration
GPV	Global Pharmacovigilance
HPV	human papillomavirus
HRT	hormonal replacement therapy
hSBA	serum bactericidal assay using human complement
ICF	Informed Consent Form
ICH	International Council for Harmonisation

IEC	Independent Ethics Committee
IMD	invasive meningococcal disease
IMP	investigational medicinal product
IRB	Institutional Review Board
IRT	interactive response technology
IU	international units
LLOQ	lower limit of quantification
LLT	lowest level term
MAAE	Medically attended adverse event
MedDRA	Medical Dictionary for Regulatory Activities
MenC	meningococcal serogroup C conjugate vaccine
NA	Not applicable
NC	Not computed
NIMP	non-investigational medicinal product
PPAS	Per-Protocol Analysis Sets
PPASC	Per-Protocol Analysis Set for concomitant vaccines
PPASM	Per-Protocol Analysis Set for meningococcal vaccines
PRN	pertactin
PT	pertussis toxoid
RCDC	Reverse cumulative distribution curve
rSBA	serum bactericidal assay using baby rabbit complement
SAE	Serious adverse events
SafAS	Safety analysis set
SAP	Statistical analysis plan
SmPC	summary of product characteristics
SOC	(Primary) System organ class
PT	Preferred term
Tdap	tetanus, diphtheria, and acellular pertussis
Tdap-IPV	tetanus, diphtheria, and acellular pertussis - inactivated polio vaccine [adsorbed, reduced antigen(s) content]
TLF	Tables, listings and figures
VLP	virus-like particle

ULOQ	Upper level of quantitation
WHO	World Health Organization
WOCBP	Woman of Childbearing Potential

7 References

1. Newcombe RG. Two-sided confidence intervals for the single proportion: comparison of seven methods. *Statistics in medicine*. 1998;17(8):857-72.
2. Newcombe RG. Interval estimation for the difference between independent proportions: comparison of eleven methods. *Stat Med*. 1998;17(8):873-90.
